2 ANALYSIS POPULATIONS

The following populations for analyses are defined.

Table 3 - Populations for analyses

Population	Description
Screened	All participants who signed the ICF.
Randomized	All participants from the screened population who have been allocated to a randomized intervention by IRT regardless of whether the intervention was received.
Exposed	All screened participants who have taken at least 1 dose of study intervention.
Intent-to-treat (ITT)	All randomized participants. Participants will be analyzed according to the intervention allocated by randomization.
Modified Intent-to-treat (mITT)	All randomized participants who either died or have available baseline and at least one post-baseline ALSFRS-R assessment
Safety	All randomized participants who receive at least 1 dose (including partial dose) of the study intervention.
Pharmacokinetic (PK)	All randomized participants who receive at least 1 dose of the study intervention and have at least 1 PK assessment with adequate documentation of dosing and sampling dates and times. Participants will be analysed according to the intervention they actually received.

ICF = informed consent form; IRT = interactive response technology; ITT = intent-to-treat; PK = pharmacokinetic

Participants exposed to study intervention before or without being randomized will not be considered randomized and will not be included in any analysis population. The safety experience of these participants will be reported separately.

Randomized participants for whom it is unclear whether they took the study intervention will be considered as exposed and will be included in the safety population as randomized.

For any participant randomized more than once, only the data associated with the first randomization (except if the first randomization is done by error) will be used in any analysis population. The safety experience associated with any later randomization will be reported separately.

For participants receiving more than one study intervention during the study, the intervention group for as-treated analyses will be SAR443820 20 mg BID.

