## 6 STUDY INTERVENTION(S) AND CONCOMITANT THERAPY

Study intervention is defined as any investigational intervention(s), marketed product(s), placebo, or medical device(s) intended to be administered to a study participant according to the study protocol. In this study, the study intervention includes SAR443820 and placebo.

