1 INTRODUCTION

1.1 STUDY DESIGN

This is a Phase 2, multicenter, randomized, double-blind, placebo-controlled, 2 parallel-group study to evaluate the efficacy and safety of SAR443820 in adult participants with amyotrophic lateral sclerosis, followed by an open-label extension.

Part A is a 24-week, double-blind, placebo-controlled part, preceded by a screening period of up to 4 weeks before Day 1. After a screening phase of up to 4 weeks, participants will be randomized in a ratio of 2:1 to receive 20 mg BID SAR443820 (n=174) or placebo BID (n=87). Randomization will be stratified by the geographic region of the study site (Asia, Europe or North America), region of ALS onset (bulbar or other areas), use of riluzole (yes or no), use of edaravone (yes or no), and use of the combination of sodium phenylbutyrate and taurursodiol (named Relyvrio in the USA and Albrioza in Canada) (yes or no). Participants will attend in-clinic study assessments at baseline (Day 1), Week 2, Week 4, Week 6, Week 8, Week 10, Week 12, Week 16, Week 20 and Week 24. All ongoing participants at Week 24 will rollover to open-label extension Part B. Participants who discontinue the treatment or choose not to enter Part B will have their follow up visit 2 weeks after the last dose of the study intervention.

Part B is an open-label, long-term extension of Part A, which starts from Week 24 and continues up to Week 106. The study intervention assignment of participants at randomization in Part A will remain blinded to Investigators, participants, and site personnel until the end of Part B unless there is medical need to unblind the study intervention assignment. All participants will receive 20 mg BID SAR443820 in Part B starting from Week 24, except those who discontinue IMP treatment permanently in Part A. Based on a data review, and in accordance with Data Monitoring Committee (DMC) recommendations, sites have been instructed on 5th December 2023 to pause the administration of SAR443820 in Part B (open-label extension) immediately. All participants in Part B will be encouraged to continue follow-up visits, but no doses of SAR443820 should be administered. Rollover to Part B for follow-up visits after completing Part A is also encouraged, but without taking SAR443820 in Part B. The decision of whether resuming SAR443820 administration in Part B will be made based on DMC recommendation when Part A data is available and benefit risk evaluation is made.

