3 STATISTICAL ANALYSES

3.1 GENERAL CONSIDERATIONS

In general, continuous data will be summarized using the number of observations available, mean, standard deviation (SD), median, interquartile range (Q1, Q3), minimum, and maximum.

Categorical and ordinal data will be summarized using the count and percentage of participants.

Efficacy data will be analyzed in the ITT population, except CAFS endpoints in Part A and Part B will be analyzed in the mITT population. Safety data will be analyzed in the safety population, unless specified otherwise.

In Part A, baseline values are defined as follows. The baseline values of NFL, CHI3L1, the cytokine and chemokine panel in serum, sTREM2 in plasma and $p75^{ECD}$ in urine, are defined as the average value from samples collected at the screening visit and at Day 1 prior to the first dose of the study intervention. For the C-SSRS, the baseline value will be the worst assessment between the past 6 months evaluation at screening and the since last visit evaluation on Day 1. For the other efficacy and safety assessments, the baseline values are defined as the last available value prior to the first dose of study intervention. For participants randomized but not treated, the baseline value is defined as the last available value before randomization. Unless otherwise indicated, 2-sided p-values and 95% confidence intervals [CI(s)] will be provided for efficacy assessment of treatment differences. Unless otherwise specified, analyses will be performed by treatment group (and overall for baseline and demographics characteristics).

Efficacy analyses in Part B will be conducted accumulatively according to the treatment group allocated by randomization in Part A (ie, Placebo/SAR443820 versus SAR443820/SAR443820). Baseline values defined above for Part A will be used as the baseline in the efficacy analyses for Part B, unless otherwise noted. Safety analyses in Part B are stated in [Section 3.6](#).

Observation period

The observation period for safety will be divided into 4 segments:

- The **pre-treatment period** is defined as the period up to first investigational medicinal product (IMP) administration.
- The **on-treatment period** (ie, treatment-emergent (TE) period) **for the Part A** is defined as the period from the first IMP administration to the earliest of 1) last IMP administration + 14 days, 2) first IMP in Part B, 3) death date, or 4) last contact date.

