3.6 SAFETY ANALYSES

All safety analyses will be performed on the safety population as defined in [Section 2](#), unless otherwise specified, using the following common rules:

- The analysis of the safety variables will be essentially descriptive, and no testing is planned.
- Safety data in participants who do not belong to the safety population (eg, exposed but not randomized) will be provided separately.

In Part A safety analysis, the safety analyses will be carried out with patients by the actual treatment received, irrespective of the treatment the patient has been randomized to.

Part A + Part B Safety Analyses

For categorical safety measures, such as AE, PCSA, shift summaries, data throughout both Part A and Part B will be summarized in three groups:

- Placebo/SAR443820 group includes participants who actually received placebo in Part A and SAR443820 in Part B. For participants in this group, only the data during SAR443820 exposure in Part B will be summarized. The baseline will be defined as the last available value prior to the first dose of SAR443820 in Part B.
- SAR443820/SAR443820 group includes participants who actually received SAR443820 in Part A, regardless of whether they entered Part B. For participants in this group, all data during SAR443820 exposure will be summarized. The baseline will be defined as the last available value prior to the first dose of the study intervention (same baseline defined for Part A in [Section 3.1](#)).
- Overall SAR443820 group includes participants from Placebo/SAR443820 group and SAR443820/SAR443820 group.

For continuous safety measures collected at longitudinal time point, such as labs and vital signs, data throughout both Part A and Part B will be summarized in two groups:

- Placebo/SAR443820 group includes participants who actually received placebo in Part A, regardless of whether they entered Part B. For participants in this group, all data during the on-treatment period of Part A and Part B will be summarized at each

protocol scheduled visit. The baseline will be defined as the last available value prior to the first dose of study intervention (same baseline defined for Part A in [Section 3.1](#)).

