3.6.1 Extent of exposure

The extent of IMP exposure will be assessed by the duration of IMP exposure and summarized within the safety population.

Duration of IMP exposure

Duration of IMP exposure in Part A is defined as last IMP administration date in Part A – first IMP administration date + 1 day, regardless of unplanned intermittent discontinuations. If the date of the last dose of IMP in Part A is missing, the duration of IMP exposure in Part A will be left as missing.

Duration of cumulative SAR443820 exposure in Part A + Part B is defined as last dose date of SAR443820 – first dose date of SAR443820 + 1 day, regardless of unplanned intermittent discontinuations. If the last dose date of SAR443820 is missing, this duration will be left as missing.

Duration of IMP exposure in Part A will be summarized quantitatively and categorically by the treatment group participants actually received in Part A (Placebo versus SAR443820):

- > 0 and \leq 4 weeks
- > 4 and \leq 8 weeks
- > 8 and \leq 12 weeks
- > 12 and \leq 16 weeks
- > 16 and \leq 20 weeks
- > 20 and \leq 24 weeks
- > 24 weeks

Duration of cumulative SAR443820 exposure in Part A + Part B will also be summarized quantitatively and categorically by actual treatment group (Placebo/SAR443820, SAR443820/SAR443820 and overall) within the safety population:

- > 0 and \leq 4 weeks

- > 4 and ≤ 8 weeks
- > 8 and ≤ 12 weeks
- > 12 and ≤ 16 weeks
- > 16 and ≤ 20 weeks
- > 20 and ≤ 24 weeks
- > 24 and ≤ 52 weeks
- > 52 and ≤ 76 weeks
- > 76 and ≤ 104 weeks
- > 104 weeks

Additionally, the cumulative duration of treatment exposure (expressed in participant-years) will be provided for Part A and Part A + Part B separately.

Treatment compliance

A given administration will be considered noncompliant if the participant did not take the number of administrations as required by the protocol. No imputation will be made for participants with missing or incomplete data.

Percentage of treatment compliance for a participant will be defined as the number of administrations that the participant was compliant divided by the total number of administrations that the participant was planned to take from the first administration of IMP up to the actual last administration of IMP.

Treatment compliance will be summarized quantitatively and categorically ($<80\%$, $\geq 80\%$) for Part A and Part A + Part B using the similar format as stated above for exposure.

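### The SAP's rule for participants who received both interventions is not limited to Part A, so read literally it moves placebo participants who took SAR443820 in Part B into the SAR443820 column of Part A safety and PD tables

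*SAP*

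**What the plan says.** SAP section 2 (Analysis populations) closes with a rule for anyone exposed to both interventions: "For participants receiving more than one study intervention during the study, the intervention group for as-treated analyses will be SAR443820 20 mg BID". Protocol section 6 makes clear that placebo counts: "In this study, the study intervention includes SAR443820 and placebo".

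SAP 1.1 describes the planned switch at the end of Part A: "All participants will receive 20 mg BID SAR443820 in Part B starting from Week 24", except for those who permanently stopped IMP in Part A. It also records the 5 December 2023 pause: "Rollover to Part B for follow-up visits after completing Part A is also encouraged, but without taking SAR443820 in Part B".

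The grouping statements elsewhere in the SAP are these:

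- **3.6, Part A safety:** "the safety analyses will be carried out with patients by the actual treatment received, irrespective of the treatment the patient has been randomized to". The sentence opens by saying that it concerns the Part A safety analysis, but it does not say that the treatment is the one received in Part A.
- **3.6, Part A + Part B categorical safety:** the switchers have their own group. "Placebo/SAR443820 group includes participants who actually received placebo in Part A and SAR443820 in Part B".
- **3.6.1, Part A exposure:** summarised "by the treatment group participants actually received in Part A (Placebo versus SAR443820").
- **3.7.1.2, PD parameters other than NfL:** summarised for Part A by actual treatment group, with no further definition.

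SAP 3.1 ends the Part A on-treatment period at the earliest of several dates, one of which is "2) first IMP in Part B".

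**The concern.** In most parallel-group trials, a rule that sends anyone with mixed exposure to the active arm catches a few dispensing errors. Here the design itself gives placebo participants the active drug at Week 24. A rule that looks across the whole study therefore catches each placebo participant who took a Part B dose, and it lets an event after Part A decide that person's column in a Part A table. If dosing resumed, more participants would meet the rule, and a Part A table produced at a later lock could differ from one produced at the Part A lock.

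The Part A safety tables carry the randomised comparison for liver events, and protocol 2.3.1 lists ALT increase/DILI as an identified risk. Moving placebo participants with placebo-period data into the SAR443820 column would dilute that column. It would also leave a small, selected placebo column: those who stopped IMP in Part A, those who did not enter Part B, and those who rolled over after the pause. Protocol 7.1.1 makes abnormal liver tests that meet the stopping criteria a reason for permanent discontinuation, so that remainder could be enriched for liver events. Both effects would tend to narrow a true difference.

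**Working it through.** **1. Planned arms.** SAP section 4 gives N = 261, and SAP 1.1 gives 2:1 allocation with 174 and 87. Check: 261 × 2/3 = 174 and 261 × 1/3 = 87. The stated figures reproduce.

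**2. Does a switcher meet the section 2 rule?** Placebo is a study intervention (protocol 6). SAR443820 taken in Part B is a second one. Part B is part of the study (SAP 1.1). All the conditions in the sentence are met, and it contains no limit to Part A.

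**3. Does other text override it?**

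| SAP text | Limits the treatment to Part A? | Applies to |
|---|---|---|
| Section 2, mixed-exposure rule | No; looks across the study | As-treated analyses in general |
| 3.6, Part A sentence | Names the Part A analysis, not treatment received in Part A | Part A safety tables |
| 3.6, three-group and two-group definitions | Yes, part by part | Part A + Part B tables only |
| 3.6.1 | Yes | Part A exposure; compliance follows a similar format |
| 3.7.1.2 | No | Part A PD summaries |
| 3.1, on-treatment period | Sets the time window, not the column | Part A events |

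For the Part A adverse event, PCSA, liver and PD tables, no text expressly sets the section 2 rule aside. The exposure table and the safety tables could therefore show different group sizes for the same people in the same period.

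**4. Who can be affected.** Only placebo participants who took SAR443820 in Part B. The first randomisation was on 28 April 2022 (SAP version history). The protocol's amendment 05 summary says that everyone had passed Week 19 by 5 December 2023. Going back 19 × 7 = 133 days, the last randomisation was by about 25 July 2023, which is 453 days after the first. Reaching Week 24 by the pause needs 24 × 7 = 168 days, so randomisation by about 20 June 2023, which is day 418. If enrolment had been uniform up to the latest possible date (an assumption), 418/453 = 92.3% would have been randomised early enough. The documents give neither the accrual pattern nor the share of placebo participants who took a Part B dose.

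**5. Size, for illustration.** Let m be the number of placebo participants who took Part B drug. The columns become 174 + m and 87 − m.

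| Assumed share of 87 | m | SAR443820 column | Placebo column |
|---|---|---|---|
| 25% | 22 | 196 | 65 |
| 50% | 44 | 218 | 43 |
| 80% | 70 | 244 | 17 |

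**6. Effect on a risk difference.** Suppose moved participants and remaining placebo participants share the same Part A placebo event rate (an assumption that ignores the selection described above). The observed difference is then the true one multiplied by 174/(174 + m): 174/196 = 0.89, 174/218 = 0.80 and 174/244 = 0.71. With assumed rates of 15% and 5%, a true difference of 10.0 points would appear as 8.9, 8.0 and 7.1 points.

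**The case against.** The strongest reply is that nobody would program the rule this way. The section 2 sentence follows paragraphs on irregular cases (exposed without randomisation, uncertain intake, randomised twice), so it can be read as covering mis-dosing and not the planned switch. SAP 3.6 never uses the as-treated label, and its sentence is introduced as applying to Part A, so the natural reading is treatment received in that part. SAP 3.6 also defines a Placebo/SAR443820 group by what was received in each part, which would have little purpose if switchers were simply SAR443820 participants. A specific rule should prevail over a general one.

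Most of this stands as evidence of intent. It does not settle the text. The part-specific groups in 3.6 are confined to Part A + Part B, the SAP states no order of precedence, and section 2 is its only stated rule for placing a mixed-exposure participant in one as-treated group.

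Three stronger inferences do not stand:

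- **That every placebo participant who rolled over is affected.** Those who rolled over after the pause took no SAR443820, so they received one intervention unless dosing resumes.
- **That the sponsor has settled on moving these participants.** SAP 3.6 and 3.6.1 point the other way, so this is a conflict between sections.
- **That the DMC's liver review would rest on mislabelled tables.** Protocol 10.1.5.2 refers DMC processes to a charter and has an independent statistician run the analysis. SAP 3.8 puts the futility interim details in a separate DMC SAP. Nothing in the documents shows that DMC outputs use the section 2 rule.

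**Conclusion.** The section 2 rule is wrong as written for Part A. Followed literally, it gives a Part A safety and PD grouping that contradicts 3.6.1 and the part-by-part logic of 3.6. The likely intent is clear enough that a careful programmer may avoid the error, but a plan for the final Part A analysis should not depend on that.

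The reach is limited. Only the column is at risk: events after the first Part B dose are already outside the Part A period. Efficacy, including NfL, is analysed in the ITT or mITT population and is not affected.

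The size cannot be fixed from the documents. The columns of 196/65, 218/43 and 244/17 rest on assumed shares of 25%, 50% and 80%. The retained fractions of 0.89, 0.80 and 0.71 rest also on equal placebo event rates in those moved and those remaining. The planned 174 and 87 stand in for actual arm sizes.

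**What to change.** Make three wording changes in the SAP:

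1. In section 2, replace *during the study* with *during Part A* in the mixed-exposure rule.
2. In 3.6, add *in Part A* after *actual treatment received* in the Part A sentence. Have the Part A PD summaries in 3.7.1.2 use the same definition.
3. State that the Part A + Part B safety groups follow the definitions in 3.6.

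With these changes the planned Part A columns stay at 174 and 87, apart from any dispensing errors within Part A, which the rule would still handle. The cost is a few words. No new data or analysis is needed, and the result agrees with what 3.6.1 already says. The change should be made, or recorded as a clarification, before the Part A tables are produced.

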3 STATISTICAL ANALYSES

3.1 GENERAL CONSIDERATIONS

In general, continuous data will be summarized using the number of observations available, mean, standard deviation (SD), median, interquartile range (Q1, Q3), minimum, and maximum.

Categorical and ordinal data will be summarized using the count and percentage of participants.

Efficacy data will be analyzed in the ITT population, except CAFS endpoints in Part A and Part B will be analyzed in the mITT population. Safety data will be analyzed in the safety population, unless specified otherwise.

In Part A, baseline values are defined as follows. The baseline values of NFL, CHI3L1, the cytokine and chemokine panel in serum, sTREM2 in plasma and $p75^{ECD}$ in urine, are defined as the average value from samples collected at the screening visit and at Day 1 prior to the first dose of the study intervention. For the C-SSRS, the baseline value will be the worst assessment between the past 6 months evaluation at screening and the since last visit evaluation on Day 1. For the other efficacy and safety assessments, the baseline values are defined as the last available value prior to the first dose of study intervention. For participants randomized but not treated, the baseline value is defined as the last available value before randomization. Unless otherwise indicated, 2-sided p-values and 95% confidence intervals [CI(s)] will be provided for efficacy assessment of treatment differences. Unless otherwise specified, analyses will be performed by treatment group (and overall for baseline and demographics characteristics).

Efficacy analyses in Part B will be conducted accumulatively according to the treatment group allocated by randomization in Part A (ie, Placebo/SAR443820 versus SAR443820/SAR443820). Baseline values defined above for Part A will be used as the baseline in the efficacy analyses for Part B, unless otherwise noted. Safety analyses in Part B are stated in [Section 3.6](#).

Observation period

The observation period for safety will be divided into 4 segments:

- The **pre-treatment period** is defined as the period up to first investigational medicinal product (IMP) administration.
- The **on-treatment period** (ie, treatment-emergent (TE) period) **for the Part A** is defined as the period from the first IMP administration to the earliest of 1) last IMP administration + 14 days, 2) first IMP in Part B, 3) death date, or 4) last contact date.
- The **on-treatment period** (ie, treatment-emergent (TE) period) **for the Part B** is defined as the period from the first IMP administration in Part B to the earliest of 1) last IMP administration + 14 days, 2) death date, or 3) last contact date.
- The **post-treatment period**, if applicable, is defined as the period from the end of the on-treatment period to the last contact date.

The on-study period is defined as the time from randomization until the end of the study defined as the last scheduled visit for those who completed the study and the end-of-study date collected

on electronic case report form (e-CRF) page “Completion of End of Study” for those who did not complete the study. If death is the end-of-study reason, date of death will be used.

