**Main secondary endpoints in Part A:** The key secondary efficacy endpoints include the combined assessment of function and survival (CAFS) score at Week 24, and change from baseline in slow vital capacity (SVC), muscle strength, Amyotrophic Lateral Sclerosis Assessment Scales - 5 items (ALSAQ-5), and serum NfL to Week 24. All the secondary efficacy endpoints will be analyzed based on the ITT population.

[figure not shown]
For continuous variables, an MMRM approach under the missing at random (MAR) assumption will be used. This model will include the fixed effect of treatment (SAR443820 or placebo), visit as a categorical variable, baseline value of the endpoint, baseline NfL (if different from the baseline value of the endpoint), randomization strata of the geographic region of the study site, ALS onset region (bulbar or other areas), use of riluzole (yes or no), use of edaravone (yes or no), use of the combination of sodium phenylbutyrate and taurursodiol (yes vs no), treatment-by-visit interaction, baseline value of endpoint-by-visit interaction and baseline NfL-by-visit interaction (if different from the baseline value of the endpoint-by-visit interaction). The primary comparison of interest will be the difference between SAR443820 and placebo at Week 24, carried out using contrast within the treatment-by-time interaction term.

**Primary endpoint in Part B:** The primary endpoint in Part B is the CAFS at Week 52. Comparison will be conducted between participants who receive SAR443820 and those who receive placebo in Part A.

**Data Monitoring Committee:** Yes

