**Table 6 - Populations for analyses**

Population	Description
Screened	All participants who signed the ICF.
Randomized	All participants from the screened population who have been allocated to a randomized intervention by IRT regardless of whether the intervention was received.
Exposed	All screened participants who take at least 1 dose of the study intervention.
Intent-to-treat (ITT)	All randomized participants. Participants will be analyzed according to the intervention allocated by randomization.
Safety	All randomized participants who receive at least 1 dose (including partial dose) of the study intervention.
Pharmacokinetic (PK)	All randomized participants who receive at least 1 dose of the study intervention and have at least 1 PK assessment with adequate documentation of dosing and sampling dates and times. Participants will be analyzed according to the intervention they actually received.

ICF = informed consent form; IRT = interactive response technology; ITT = intent-to-treat; PK = pharmacokinetic

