#### **9.4.3 Secondary endpoint(s) in Part A**

The key secondary efficacy endpoints include the CAFS at Week 24, and change from baseline in SVC, change from baseline in muscle strength, ALSAQ-5, and serum NfL to Week 24. All secondary efficacy endpoints will be analyzed based on the ITT population.

For continuous variables, an MMRM approach under the MAR assumption will be used. This model will include the fixed effect of treatment (SAR443820 or placebo), visit as a categorical variable, baseline value of the endpoint, baseline NfL (if different from the baseline value of the endpoint), randomization strata of the geographic region of the study site, ALS onset region (bulbar or other areas), use of riluzole (yes or no), use of edaravone (yes or no), use of the combination of sodium phenylbutyrate and taurursodiol (yes vs no), treatment-by-visit interaction, and baseline value of the endpoint-by-visit interaction and baseline NfL-by-visit interaction (if different from the baseline value of the endpoint-by-visit interaction). The primary comparison of interest will be the difference between SAR443820 and placebo at Week 24, carried out using contrast within the treatment-by-time interaction term. Available data will be used for all secondary analyses.

To have strong control of the Type I error rate, a closed sequential testing approach will be used. The order of the secondary efficacy endpoints and all the details of sequential testing will be specified in the full SAP. The details of the analysis for other secondary endpoints will be outlined in the full SAP.

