3.5 MULTIPLICITY ISSUES

To control the Type 1 error rate for the study, a hierarchical testing procedure will be applied at a 2-sided 5% significance level for primary and selected secondary endpoints in Part A, ie, each hypothesis will be formally tested only if the preceding one is significant at the 5% level. If

SAR443820 is significant for the primary endpoint in part A, a selective set of secondary endpoints in Part A will be tested following the hierarchical testing procedure shown below:

- CAFS score at Week 24
- Change from baseline in ALSAQ-5 to Week 24
- Change from baseline in serum NfL to Week 24
- Change from baseline in SVC to Week 24
- Change from baseline in megascore to Week 24

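### The SAP analyses CAFS at Week 24, the first gated secondary endpoint, in an mITT set that keeps every death and drops living participants without scores, where the protocol specifies ITT

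*SAP*

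**What the plan says.** **Protocol.** Section 9.4.3 states that "The key secondary efficacy endpoints include the CAFS at Week 24" and then that "All secondary efficacy endpoints will be analyzed based on the ITT population". The synopsis repeats it: "All the secondary efficacy endpoints will be analyzed based on the ITT population". Table 6 defines ITT as "All randomized participants. Participants will be analyzed according to the intervention allocated by randomization", and contains no modified ITT set. Section 9.4.4, on CAFS at Week 52 in Part B, names no population.

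**SAP.** Table 3 adds an mITT set: "All randomized participants who either died or have available baseline and at least one post-baseline ALSFRS-R assessment". Section 3.1 puts efficacy data in ITT "except CAFS endpoints in Part A and Part B will be analyzed in the mITT population". Table 2 gives mITT for CAFS at Week 24 under a treatment policy label, and 3.2.2 uses mITT for CAFS at Week 52. In 3.5, "a selective set of secondary endpoints in Part A will be tested following the hierarchical testing procedure shown below", and CAFS at Week 24 heads that list, ahead of ALSAQ-5, serum NfL, SVC and megascore. The rule is that "each hypothesis will be formally tested only if the preceding one is significant at the 5% level".

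**CAFS scoring (SAP 3.2.1).** The survival endpoint is death or permanent assisted ventilation. An early discontinuer is compared on time to death when the comparator died, and otherwise at the last ALSFRS-R time-point that both have. A tie scores 0.

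**The concern.** The two documents name different populations for the same endpoint, and that endpoint is a gate. If the primary endpoint succeeds, the CAFS test decides whether four further endpoints can be tested formally. A dispute over which population was prespecified would therefore reach beyond CAFS.

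The substitute set also selects on what happens after randomization, and unevenly. Among participants with no post-baseline ALSFRS-R, those who died stay and those still alive leave. If early loss differs between arms, the groups compared are no longer the groups randomized. This fits poorly with the treatment policy label in Table 2.

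**Working it through.** **1. The texts side by side**

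| Item | Protocol | SAP |
|---|---|---|
| Population for CAFS at Week 24 | ITT (9.4.3, synopsis) | mITT (3.1, Table 2) |
| mITT defined? | No (Table 6) | Yes (Table 3) |
| Population for CAFS at Week 52 | None named (9.4.4) | mITT (3.1, 3.2.2) |
| Change or reason listed | n/a | None visible (version history, 3.9) |

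The direct contradiction is therefore for Week 24.

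**2. Who is in the mITT set**

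- Died, no post-baseline score: in, whenever the death occurred. Someone alive at Week 24 without scores who died later would enter the Week 24 set.
- Alive, baseline and at least one post-baseline score: in.
- Alive, no post-baseline score: out.
- Alive, reached permanent assisted ventilation, no post-baseline score: out, despite having a survival event by SAP 3.2.1.
- Alive, no baseline score: out. This group should be almost empty, because inclusion criterion I 04 needs a screening ALSFRS-R.

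**3. The plan's own figures.** No size is given for the mITT set. The visible arithmetic agrees: 261 × 2/3 = 174, 261/3 = 87, and 261/0.8 = 326 screened. The power behind 261 cannot be recomputed, because the placebo change and SD are redacted.

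**4. Set size and death share (assumed exclusions, SAR443820 + placebo)**

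- About 1%: 261 − (2 + 1) = 258.
- About 5%: 261 − (9 + 4) = 248.
- About 10%: 261 − (17 + 9) = 235.

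With an assumed 9 deaths on SAR443820, the death share is 9/174 = 5.17% in ITT. In mITT it becomes 9/172 = 5.23%, 9/165 = 5.45% and 9/157 = 5.73%, because the deaths stay while the denominator shrinks.

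**5. Power.** The simulations used 174/87, 5% deaths, a 1.8-point effect, pairwise CAFS scores and a Mann-Whitney test, with 3,000 trials per scenario in the tabled runs. All are assumptions apart from the arm sizes, the scoring and the test. The SDs of 4.6 and 4.7 are plausible. Two-sided 5% and 80% power imply δ/SD = 2.802 × √(1/69.6 + 1/139.2) = 0.411 after 20% drop-out, or 0.368 without it. A 1.8-point effect then implies an SD between 1.8/0.411 = 4.4 and 1.8/0.368 = 4.9. Early loss is unrelated to outcome.

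| Early loss, SAR443820 v placebo | ITT with ties | mITT |
|---|---|---|
| 2% v 2% (SD 4.6) | 72.8% | 72.7% |
| 10% v 2% (SD 4.6) | 73.9% | 71.1% |
| 10% v 2% (SD 4.7) | 70.6% | 67.9% |

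The Monte Carlo standard error of each figure is about √(0.7 × 0.3/3000) = 0.8 points. With 10% lost in both arms (SD 4.7) the two analyses agree within 0.3 points. A further run at SD 4.7 gave under 1 point of difference at 2-5% loss, and about 2 points at 10% v 2%.

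**6. Type I error and direction.** Null simulation, 4,000 trials per scenario, exclusions on SAR443820 only. The Monte Carlo standard error is √(0.05 × 0.95/4000) = 0.34 points.

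| Excluded | mITT type I error, random leavers | mITT type I error, leavers from worse half of the living | Probability that SAR443820 ranks better (worse half) |
|---|---|---|---|
| 2% | 4.8% | 4.7% | 0.503 |
| 5% | 5.2% | 6.2% | 0.512 |
| 10% | 4.8% | 8.6% | 0.523 |

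With random leavers the ranking probability falls by at most about 0.002, against SAR443820. With sicker leavers it moves the other way. Scoring those leavers as ties does not cure this: two further runs with sicker leavers gave type I errors of 8.3% and 9.6% for ITT with ties, against 7.1% and 7.7% for mITT.

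**The case against.** **Few participants should be affected.** Exclusion needs a living participant with no post-baseline ALSFRS-R at all. The first scheduled score is at Week 4, the early discontinuation visit appears to collect it too, people off drug are still followed with it, and remote collection is allowed. A 10% loss on SAR443820 would be half of the planned 20% drop-out. This stands, and is why the effect is called small.

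**Ties are also an assumption.** They give a sick early leaver a middling rank among survivors, and vital status (Protocol 7.4) is only attempted within legal and ethical limits. This stands: the case for ITT is that the protocol states it, not that it removes bias. A scoring rule is needed in any case, because the SAP's own set can admit someone alive and unscored at Week 24 who died later.

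**Stronger readings that the documents do not support:**

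- *The change was concealed.* The SAP states the mITT choice openly in 3.1, Table 2 and 3.2.2. Section 3.9 opens by limiting itself to protocol amendments, and the version history has a redacted entry. Only the visible text is silent.
- *No ITT analysis of CAFS exists.* The text of SAP 3.2.3 is not shown. The one visible CAFS sensitivity analysis (3.3.1.3) is in mITT, but that does not settle what 3.2.3 contains.
- *mITT works against the arm with more withdrawal.* That holds only when leaving is unrelated to prognosis.
- *Part B contradicts the protocol as well.* Protocol 9.4.4 names no population.

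**Conclusion.** The contradiction for CAFS at Week 24 is certain from the text. The mITT definition is also flawed in itself: it selects on post-randomization data, sets no time limit on the death criterion, and ignores permanent assisted ventilation.

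The likely numerical effect is small: nothing material at 2-5% early loss, and about 2 to 3 points of power at an assumed 10% versus 2%. Type I error stays near 5% when leaving is unrelated to outcome. It rises to 6.2-8.6% for mITT only if 5-10% of one arm leave early and come from its sicker survivors. These figures rest on assumed death rates, SD, effect and loss rates, since the documents give no early-loss rate and redact the SD and placebo change.

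The point deserves correction because it concerns the prespecification of a gatekeeper and is cheap to settle. It does not show that the CAFS test is invalid.

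**What to change.** - In SAP 3.1 and Table 2, make ITT the main population for CAFS at Week 24, as the protocol states.
- In 3.2.1, extend the existing pairwise rule to a living participant with no post-baseline score: better than anyone with an earlier survival event, and 0 against every other survivor. This follows from the last-common-time-point rule, because baseline is then the only shared point and both changes are zero.
- State in the pairwise rule that permanent assisted ventilation counts as a survival event. The endpoint definition includes it, but the pairwise wording speaks only of death.
- State a rule for unknown vital status, for example censoring at last contact: better than anyone with an event before that date, otherwise 0.
- Keep mITT as a sensitivity analysis, and record the populations and the reason in the list of changes.
- For consistency, use the same population for the Part B CAFS. The protocol leaves this open.
- Report by arm the number of living participants without a post-baseline score.

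The cost is SAP wording and a few lines of code, before the Part A database lock. The downsides are a few more ties, and that informative early dropout remains, which is why early loss should be reported by arm.
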